ECG	Electrocardiogram
ICH	International Conference on Harmonization of Technical Requirements for Registration of Pharmaceuticals for Human Use
IEC	Independent Ethics Committee
i.v.	Intravenous
IRB	Institutional Review Board
MMSE	Mini-Mental State Examination
o.d.	once a day
p.o.	oral
SAE	serious adverse event

Glossary of terms

Assessment	A procedure used to generate data required by the study
Control drug	Drugs(s) used as a comparator to reduce assessment bias, preserve blinding of investigational drug, assess internal study validity, and/or evaluate comparative effects of the investigational drug
Enrollment	Point/time of patient entry into the study; the point at which informed consent must be obtained (i.e. prior to starting any of the procedures described in the protocol)
Epoch	The planned stage of the subjects' participation in the study. Each epoch serves a purpose in the study as a whole. Typical epochs are: determination of subject eligibility, wash-out of previous treatments, exposure of subject to treatment or to follow-up on subjects after treatment has ended.
Investigational drug	The drug whose properties are being tested in the study; this definition is consistent with US CFR 21 Section 312.3 and is synonymous with "investigational new drug" or "investigational medicinal product."
Investigational treatment	All investigational drug(s) whose properties are being tested in the study as well as their associated treatment controls. This includes any placebos, any active controls, as well as approved drugs used outside of their indication/approved dosage or tested in a fixed combination. Investigational treatment generally does not include other treatments administered as concomitant background therapy required or allowed by the protocol when used within approved indication/dosage
Medication number	A unique identifier on the label of each investigational/study drug package in studies that dispense medication using an IRT system
Subject Number	A number assigned to each patient who enrolls into the study
Part	A subdivision of a single protocol into major design components. These parts often are independent of each other and have different populations or objectives. For example, a single dose design, a multiple dose design that are combined into one protocol, or the same design with different patient populations in each part.
Period	A subdivision of a cross-over study
Premature patient withdrawal	Point/time when the patient exits from the study prior to the planned completion of all investigational/study treatment administration and all assessments (including follow-up)
Randomization number	A unique identifier assigned to each randomized patient, corresponding to a specific treatment arm assignment
Stop study participation	Point/time at which the patient came in for a final evaluation visit or when study/investigational treatment was discontinued whichever is later
Study drug/ treatment	Any single drug or combination of drugs administered to the patient as part of the required study procedures; includes investigational drug (s), active drug run-ins or background therapy
Study/investigational treatment	Point/time when patient permanently stops taking

discontinuation	study/investigational treatment for any reason; may or may not also be the point/time of premature patient withdrawal
Variable	Information used in the data analysis; derived directly or indirectly from data collected using specified assessments at specified time points

Protocol synopsis

Protocol number	CENA713DIN01
Title	A prospective, 16 week, phase IV study to evaluate safety, tolerability and effectiveness in patients with severe dementia of the Alzheimer's type exposed to rivastigmine (Exelon)15cm ² transdermal patch
Brief title	Study of safety and effectiveness of Rivastigmine in Alzheimer patients
Sponsor and Clinical Phase	Novartis
Investigation type	Drug
Study type	Interventional
Purpose and rationale	
The present phase IV study is mandated by Indian health authority (HA) as a part of conditional approval to market authorization of rivastigmine 27 mg -15 cm² transdermal patch for treatment of severe dementia secondary to Alzheimer's disease (AD). The HA mandated phase IV study in their approval letter. Due to non-availability of Indian data for rivastigmine 27 mg -15 cm² transdermal patch in severe dementia secondary to Alzheimer's disease (AD) patients, marketing authorization of the same has been granted condition to phase IV study. As per HA letter, interventional study is to be conducted.
 
Thus the present 16 week study will be conducted to evaluate safety, tolerability and effectiveness in patients with severe dementia of the Alzheimer's type exposed to rivastigmine 27 mg -15 cm² transdermal patch as mandated by HA. Most frequent AEs in ACTION study were application site erythema/ dermatitis and UTI, the present study shall assess application site reaction and urine examination.

Primary Objective(s) and Key Secondary Objective	To obtain safety data in patients with severe dementia of the Alzheimer's type treated with rivastigmine 27 mg -15 cm ² transdermal patch for 16 weeks
Secondary Objectives	
• To assess patients compliance of rivastigmine 27 mg -15 cm² transdermal patch during 16 weeks treatment period

	
• To assess the skin tolerability (irritation and adhesion) during 16 weeks treatment period• To assess the proportion of patients with UTI during 16 weeks treatment period• To evaluate treatment effect by rivastigmine 27 mg -15 cm² transdermal patch by assessing the changes in Mini-Mental State Examination (MMSE)• To evaluate treatment efficacy by rivastigmine 27 mg -15 cm² transdermal patch by assessing the changes in ADCS-Activities of Daily Living Inventory – Severe Impairment Version (ADCS-ADL SIV) Score
Study design	
This is a multicenter, prospective, phase IV study evaluating safety, tolerability and effectiveness of rivastigmine 27 mg -15 cm² transdermal patch prescribed in patients with severe dementia of the Alzheimer's type as per discretion of treating physician.
 
The prescription decision shall be independent of decision for inclusion in the study. Patients treated according to local routine clinical practice will be enrolled in the study upon signing an Informed Consent. Eligibility for study entry will be determined by the study investigator, in accordance with the selection criteria below. Signing of the Informed Consent defines the study entry visit. Routine urine examination shall be done to detect any UTI. Compliance to treatment directions shall be reviewed by treating investigator at every visit.
 
After 8 week and at 16 week, it is expected for the physician to follow up as per routine practice in India. The treating physician will assess the safety, tolerability and effectiveness of the rivastigmine 27 mg -15 cm² transdermal patch and may consider continuing or changing the therapy

Population	Alzheimer's disease patients
Inclusion criteria	
1. Patients willing to participate in the study by providing written informed consent.2. Patients diagnosed with severe dementia secondary to Alzheimer's disease (AD)
Exclusion criteria	
1. Contraindication as per PI2. Patients simultaneously participating in other studies

Investigational and reference therapy	Rivastigmine patch 15cm2
Efficacy assessments	
• Mini-Mental State Examination (MMSE)• ADCS-Activities of Daily Living Inventory – Severe Impairment Version (ADCS-ADL SIV) Score
Safety assessments	
• Urine examination• Skin reaction at patch• Patch adhesion• Adverse events
Other assessments	
• Compliance by Caregiver medication questionnaire
Data analysis	The primary safety objective of this study will be assessed by collecting adverse events. The key secondary objective of this study will be assessed by compliance measured by caregiver questionnaire, skin reaction and change in MMSE from baseline
Key words	Alzheimer, Rivastigmine,

1 Introduction

1.1 Background

1.2 Purpose

Alzheimer's disease (AD), a progressive neurodegenerative disorder, is the most prominent cognitive disorder of the elderly. The prevalence of AD in people over the age of 65 is 5-10%, and increases up to 50% in those over the age of 85 (Small GW, 1995). The Alzheimer's Association estimates that in 2008, as many as 5.2 million Americans have AD (Alzheimer's Association, 2008).

Multiple deficits of neurotransmitters occur in the brain of AD patients. However, the most common is a decrease in levels of acetylcholine (ACh), which is due to a loss of presynaptic cholinergic nerve terminals. These cholinergic deficits are most apparent in the areas of the brain involved in memory and cognition, i.e., the frontal cortex and hippocampus (Perry et al, 1978).

Currently, there are two compounds approved in the US for the treatment of severe dementia of the Alzheimer's type, the cholinesterase inhibitor donepezil and the glutamate modifying agent memantine. Both are often used together. With only one agent in each class available to treat patients with severe dementia of the Alzheimer's type, there is significant medical need to have other approved agents available, including those that have an alternative route to oral administration.

A number of treatment strategies involving the cholinergic system have been evaluated. Cholinesterase inhibitors (ChEIs), including rivastigmine (also known as ENA713 and Exelon®), have been shown to be effective in improving cognitive and global functioning in mild to moderate AD patients (Kumar et al, 1991; Knapp et al, 1994; Rogers et al, 1998; Corey-Bloom et al, 1998; Rösler et al, 1999; Raskind et al, 2000; Tariot et al, 2000).

Memantine has established efficacy in moderate to severe dementia of the Alzheimer's type (Reisberg et al, 2003; Tariot et al, 2004; van Dyck et al, 2007) and can be used as an augmenting agent with ChEIs.

The need for effective and well-tolerated treatments for AD (both symptomatic and disease modifying) remains great. Exelon® transdermal patch, prescribed once-daily, has the potential to offer improved caregiver and patient convenience in severe dementia of the Alzheimer's type, which may contribute to an improvement in patient compliance. In addition, this formulation is useful for patients unable to take oral medication. Exelon® (rivastigmine) is a slowly reversible (pseudo-irreversible), brain selective, dual inhibitor of Acetyl cholinesterase (AChE) and Butyryl cholinesterase inhibitors (BuChE) of the carbamate type. Exelon® exerts its therapeutic effect by enhancing cholinergic function. This is accomplished by increasing the concentration of acetylcholine through reversible cholinesterase inhibition. The present study is mandated by Indian health authority (HA) as a part of conditional approval to market authorization of rivastigmine 27 mg- 15 cm² transdermal patch for treatment of severe dementia secondary to Alzheimer's disease (AD).

Thus the present 16 week study will be conducted to evaluate safety, tolerability and effectiveness in patients with severe dementia of the Alzheimer's type exposed to rivastigmine 27 mg -15 cm² transdermal patch as mandated by HA. Most frequent AEs in ACTION study were application site erythema/ dermatitis and UTI, the present study shall assess application site reaction and urine examination

2 Study objectives

2.1 Primary

Primary objective: To obtain safety data in patients with severe dementia of the Alzheimer's type treated with rivastigmine 27 mg -15 cm² transdermal patch for 16 weeks

2.2 Secondary objectives

Secondary objectives:

- To assess patients compliance of rivastigmine 27 mg -15 cm² transdermal patch during 16 weeks treatment period
- To assess the skin tolerability (irritation and adhesion) during 16 weeks treatment period
- To assess the proportion of patients with UTI during 16 weeks treatment period
- To evaluate treatment effect by rivastigmine 27 mg -15 cm² transdermal patch by assessing the changes in Mini-Mental State Examination (MMSE)
- To evaluate treatment efficacy by rivastigmine 27 mg -15 cm² transdermal patch by assessing the changes in ADCS-Activities of Daily Living Inventory – Severe Impairment Version (ADCS-ADL SIV) Score

2.3 Exploratory objectives

None

3 Investigational plan

3.1 Study design

This is a multicenter, prospective, phase IV study evaluating safety, tolerability and effectiveness of rivastigmine 27 mg -15 cm² transdermal patch prescribed in patients with severe dementia of the Alzheimer's type as per discretion of treating physician.

The prescription decision shall be independent of decision for inclusion in the study. Patients treated according to local routine clinical practice will be enrolled in the study upon signing an Informed Consent. Eligibility for study entry will be determined by the study investigator, in accordance with the selection criteria below. Signing of the Informed Consent defines the

study entry visit. Routine urine examination shall be done to detect any UTI. Compliance to treatment directions shall be reviewed by treating investigator at every visit.

After 8 week and at 16 week, it is expected for the physician to follow up as per routine practice in India. The treating physician will assess the safety, tolerability and effectiveness of the rivastigmine 27 mg -15 cm² transdermal patch and may consider continuing or changing the therapy.

3.2 Rationale of study design.

This is open label study to examine the safety, effectiveness, and tolerability of the treatment in routine clinical practice, to determine how the treatment works under ordinary and variable conditions, prescribed by clinicians with varying degrees of expertise and practicing across the spectrum of health care settings, to treat a heterogeneous group of patients.

3.3 Rationale of dose/regimen, route of administration and duration of treatment.

Dose and regimen is as per approved label in India for rivastigmine.

3.4 Rationale for choice of comparator

No comparator is used in study

3.5 Purpose and timing of interim analyses/design adaptations

Not applicable

3.6 Risks and benefits

Rivastigmine is approved for the treatment of mild to moderately severe dementia of the Alzheimer type (and in some countries mild to moderately severe dementia associated with PD and severe dementia of the Alzheimer's type). In most cases the drug is used as a monotherapy, although in some cases it is used along with memantine. Prescription of the medication is initiated at a low dose and increased according to the patient's response and tolerance. Total period prescription numbers of the oral formulations are steadily decreasing to be replaced by increasing numbers of prescriptions of the transdermal (Patch) formulations. The treatment is initiated at patch 5cm² and increased to patch 10 cm² after a minimum of four weeks of treatment if well tolerated and then, if appropriate to patch 15 cm².

The benefit of rivastigmine has been seen in multiple clinical trials, in both placebo and active-controlled trials (using low dose Exelon as the active comparator). The ability of rivastigmine to positively affect the symptoms of AD and Parkinson's disease dementia has been demonstrated in six randomized double-blind, placebo-controlled clinical trials with 4517 patients with mild to moderate AD and in one randomized double blind placebo controlled trial with Parkinson's disease dementia with 541 patients. There was one (ENA713D2340) active controlled trial in mild to moderate AD with 1582 patients. There was one active controlled trial (US44 and US44E1) with extension for severe AD.

Clinically significant improvement in AD and Parkinson's disease dementia symptoms were observed in all but one clinical trial with response rates, in the transdermal formulations, achieved predominantly in patch 10 cm² and patch 15 cm² users. Dementia improvement was seen in all tested demographics. The most frequently reported AEs were nausea, vomiting and diarrhea. This is consistent with Exelon's cholinergic effects and with results seen with Exelon® capsule. Action study with 15 cem Patch has demonstrated The 13.3 mg/24 h patch demonstrated superior efficacy to 4.6 mg/24 h patch on Severe Impairment Battery (SIB) and AD Cooperative Study—Activities of Daily Living scale—Severe Impairment Version (ADCS-ADL-SIV), without marked increase in AEs, suggesting higher-dose patch has a favorable benefit-to-risk profile in severe AD.

No pivotal clinical trials are ongoing except for CENA713D2409 which is a PASS drug utilization study to assess medication errors and misuse and multiple patch use in particular. All identified and potential risk are discussed in the Exelon RMP (version 8.0) and PSUR 24 (DLP 31 Jan 2016) and no new risks have been added and several have been removed in the last 2 PSURs. The sole risk with an ongoing risk minimization strategy is for medication errors (specifically multiple patch use) which is currently being actively implemented. Previous clinical trial results have been data-mined as a means for expanding MAH knowledge of the previously unstudied population of patients with pre-existing renal compromise and pre-existing cardiac disorders. No risk for use of rivastigmine in these populations has been detected to date. The company is continuing to investigate the increased reporting rate of skin reactions in the Japanese population which may result from intensive local pharmacovigilance collection techniques and determine if further measures are necessary.

The risk benefit ratio for Exelon (oral and transdermal formulations) remains positive.

4 Population

The study population will consist of male and female patients diagnosed with Alzheimer's disease and prescribed with rivastigmine 27mg -15 cm² transdermal patch as per discretion of treating physician. Inclusion and exclusion criteria follow the approved indication and contraindications, as mentioned in package insert (PI) in India

4.1 Inclusion criteria

Patients eligible for inclusion in this study have to fulfill all of the following criteria:

- Patients willing to participate in the study by providing written informed consent.
- Patients diagnosed with severe dementia secondary to Alzheimer's disease (AD)
- Patient's prescribed with rivastigmine 27mg -15 cm² transdermal patch as per discretion of treating physician

4.2 Exclusion criteria

Patients fulfilling **any** of the following criteria are not eligible for inclusion in this study. No additional exclusions may be applied by the investigator, in order to ensure that the study population will be representative of all eligible patients.

Exclusion criteria:

1. Contraindication as per PI
2. Patients simultaneously participating in other studies

4.3 Protocol requested treatment

4.3.1 Investigational treatment

The study will include the following open-label drug:

Exelon[©] patch: 15 cm² patch sizes loaded with 27 mg of rivastigmine

4.3.2 Additional study treatment

No additional treatment beyond investigational treatment is requested for this trial.

4.4 Treatment arms.

Single arm study

4.5 Treatment assignment, randomization.

No protocol specific treatment will be assigned to subjects.

4.6 Treating the patient

4.6.1 Patient numbering

Each patient is uniquely identified by a Subject Number which is composed by the site number assigned by Novartis and a sequential number assigned by the investigator. Once assigned to a patient, the Subject Number will not be reused.

Upon signing the informed consent form, the patient is assigned the next sequential number by the investigator. The reason for not being treated will be entered on the Screening Epoch Study Disposition CRF.

4.6.2 Dispensing the investigational treatment

Commercial Novartis drugs will be locally purchased.

4.6.3 Handling of study treatment.

Not applicable.

4.6.4 Handling of investigational treatment

Not applicable.

4.6.5 Instructions for prescribing and taking study treatment

The investigator should promote compliance by instructing the patient to take the study treatment exactly as prescribed and by stating that compliance is necessary for the patient's safety and the validity of the study. The patient should be instructed to contact the investigator if he/she is unable for any reason to take the study treatment as prescribed.

Refer to appendix 2 for instruction for applying the patch

4.6.6 Permitted dose adjustments and interruptions of study treatment

For patients who are unable to tolerate the protocol-specified dosing scheme, dose adjustments and interruptions are permitted in order to keep the patient on study drug. If necessary, the patient may be instructed to skip certain doses for a prescribed length of time (e.g., skip one or two day's doses) until tolerability has improved. The following treatment adjustment scheme is recommended:

- If tolerability problem arises: The caregiver should remove the patch(es) on the day the tolerability problems arise and skip 1 or 2 days of treatment.
- Tolerability should be reassessed after the patient has skipped the recommended days of treatment.
- If tolerability problems have improved, and consecutive days of missed doses is ≤ 3 days, treatment may be restarted at the same DL.
- If tolerability is still an issue, restart treatment at the next lower DL.
- The patient should then resume the titration schedule if tolerability issues have improved.
- If subsequent titration again leads to a tolerability problem, doses may again be skipped and the DL should be decreased to the next lower DL
- Further attempts to titrate the dose upward are at the investigator's discretion (i.e., if necessary for tolerability, titration to the target dose need not be achieved)

4.6.7 Rescue medication

Not applicable

4.6.8 Concomitant treatment

The investigator should instruct the patient to notify the study site about any new medications he/she takes after the patient was enrolled into the study. All medications, procedures and significant non-drug therapies (including physical therapy and blood transfusions) administered after the patient was enrolled into the study must be recorded.

4.6.9 Prohibited Treatment

No prohibited medication

4.6.10 Discontinuation of study treatment and premature patient withdrawal

The planned duration of the study is 16 weeks (+/- 2 weeks) and patients should be followed until the end of the study except if any of the following conditions for early termination are met:

- Voluntary discontinuation (withdrawal of consent to collect or use their data)

- Treatment discontinuation (patient no longer take the medication under observation)
- Addition of second AD treatment (patient no longer on monotherapy)

All data generated up to the time of voluntary discontinuation (withdrawal of consent) and the reason(s) for discontinuation will be recorded. Patients who choose to withdraw consent will no longer be contacted for follow up information.

Patients who discontinue treatment or patients who are no longer on monotherapy should be asked to return for an early discontinuation assessment. For patients who are lost to follow-up (i.e. those patients whose status is unclear because they fail to appear for study visits without stating an intention to withdraw), the physician should show "due diligence" by contacting the patients and asking them to return for a final assessment. Every effort should be made to obtain reason for discontinuation. The physician should document in the source documents steps taken to contact the patient, e.g. dates of telephone calls, registered letters, etc.

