4.6.13 Early study termination

The study can be terminated at any time for any reason by Novartis. Should this be necessary, the patient should be seen as soon as possible and treated for a prematurely withdrawn patient. The investigator may be informed of additional procedures to be followed in order to ensure that adequate consideration is given to the protection of the patient's interests. The investigator will be responsible for informing IRBs and/or ECs of the early termination of the trial.

5 Visit schedule and assessments

Error! Reference source not found. lists all of the assessments and indicates with an "x" when the visits are performed.

Examination	Baseline Visit 1 (Day 1)	Visit-2 (8 ± 2 weeks)	EOS Visit 3 (16 ± 2 weeks)
Informed consent	X		
Patient demographics (sex, age, etc)	X		
Relevant medical history	X		
Vitals	X	X	X
Physical examination*	X	X	X
Height** and weight	X	X	X
Inclusion/Exclusion criteria	X		
MMSE score	X	X	X
ADCS-ADL SIV score	X		X
Concomitant medications		X	X
Treatment for AD	X	X	X
Urine examination	X	X	X
Skin irritation assessment		X	X
Patch adhesion assessment		X	X
Adverse Events (AEs)and Serious Adverse Events (SAEs) recording	X	X	X
Compliance assessment using caregiver questionnaire		X	X
EOS			X

EOS = End of Study

X = Assessment to be recorded on CRF

*Physical examination includes examination of general appearance, skin, neck (including thyroid), eyes (excluding fundus), ears, nose, throat, lungs, heart, abdomen, back, lymph nodes, and extremities. In addition, a neurological exam consisting of cranial nerve, motor and sensory assessments as performed in routine clinical practice. It also includes recording of pulse and blood pressure as per routine clinical care.

** Height is assessed only at Visit 1

At a minimum, patients will be contacted for safety evaluations during the 30 days following the last study visit or following the last administration of study treatment), including a final contact at the 30-day point. Documentation of attempts to contact the patient should be recorded in the source documentation.

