5.4 Efficacy

5.4.1 Efficacy assessment

Mini-Mental State Examination (MMSE):

Assessing the changes in Mini-Mental State Examination (MMSE): The MMSE is a brief, practical screening test for cognitive dysfunction (Folstein et al. 1975). The test consists of

five sections (orientation, registration, attention-calculation, recall, and language & Praxis) and results in a total possible score of 30, with higher scores indicating better function. MMSE shall be recorded at the start and at each visit as mentioned in table 5.1as a part of routine clinical practice.

ADCS-ADL SIV score*:

This is a tool to assess the ability of patients with moderate to severe dementia to perform activities of daily living. ADCS-ADL SIV score is done at start and end of visit. This includes 19 questions and total score is 54. Administration instructions and Instruction card for the rater to use when administering the scale is separately provided

*"Used with permission from the NIA Alzheimer's Disease Cooperative Study (NIA Grant AG10483)".

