### **9.7.4 Patch adhesion assessment**

Patch adhesion assessment will be measured at Visit-2 (8 ± 2 weeks), EOS Visit 3 (16 ± 2 weeks).

A summary of these findings will be presented by number and percentages of patients using SAF population.

Data listings will be presented for Patch adhesion assessment.

	Statistical Analysis Plan Sponsor: Novartis
Study Number: [REDACTED]	Version: Final 1.0 Date: 01 Dec 2022

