**Catalogue of Tables, Listings and Figures**  
**Sponsor: Novartis**

**Study Number: EA-CT-18-001**

**Version: Final 1.0 Date: 01 Dec 2022**

**Table 14.3.8: Summary of Skin tolerability during 16 weeks treatment period**

Novartis

*ddmmmyyyy hh:mm  
Page x of y*

Table 14.3.8  
Summary of Skin tolerability during 16 weeks treatment period  
(Safety Population)

Visit	Parameter	Category	Total (N=xx) n (%)
Visit 2	Score to capture comments relating to patch adhesion	0 1 2 3 4	xx (xx.x) xx (xx.x) xx (xx.x) xx (xx.x) xx (xx.x)
	Has patch skin reaction occurred?	Yes No	xx (xx.x) xx (xx.x)
	Score to assess skin irritation (Dermal response)	0 1 2 3 4 5	xx (xx.x) xx (xx.x) xx (xx.x) xx (xx.x) xx (xx.x) xx (xx.x)
	Score to assess skin irritation (Other effects)	Yes No	xx (xx.x) xx (xx.x)
	Other effects	O P	xx (xx.x) xx (xx.x)

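### The early discontinuation assessment has no defined content and no place in the SAP, so early stoppers dilute the graded skin and adhesion percentages and have no defined functional result

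*Protocol*

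**What the plan says.** Protocol 4.6.10 names three grounds for ending follow-up early: withdrawn consent, stopping treatment, and adding a second AD treatment. For the last two it says: "Patients who discontinue treatment or patients who are no longer on monotherapy should be asked to return for an early discontinuation assessment". Patients lost to follow-up are to be asked back for a final assessment. Neither assessment is given any content. The glossary entry for stopping study participation reads "Point/time at which the patient came in for a final evaluation visit or when study/investigational treatment was discontinued whichever is later", which also names a final visit without saying what is done at it.

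Protocol section 5 introduces the schedule as a table that "lists all of the assessments and indicates with an" x when each is due. Its only columns are Baseline, Visit 2 (8 ± 2 weeks) and EOS Visit 3 (16 ± 2 weeks), and SAP 7.1.1 repeats them. Skin irritation, patch adhesion and the caregiver questionnaire (CMQ) start at Visit 2. For the functional scale, Protocol 5.4.1 says "ADCS-ADL SIV score is done at start and end of visit", and the schedule marks it at baseline and EOS only. Protocol section 10 forbids investigators to collect research data or perform research procedures beyond those in the protocol.

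On the analysis side:
- SAP 8.5.1 applies LOCF to missing week-16 values and leaves missing safety data unimputed.
- SAP 8.2 admits to the ITT set any consenting patient with a single assessment after baseline.
- Table 14.3.8, "Summary of Skin tolerability during 16 weeks treatment period", has blocks for Visit 2 and Visit 3 only. Its N is the safety population, and SAP 8.1 takes percentages relative to N.
- Table 14.2.2.1 (ADCS-ADL SIV total) has Baseline, Visit 2 and two blocks both labelled EOS. Neither EOS block is marked as early discontinuation or LOCF.

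**The concern.** The protocol brings early stoppers back to the clinic but does not tell the site what to record, and the SAP does not tell the programmer where to put it. Under section 10 of the protocol, a site that scores skin or ADCS-ADL SIV at that visit is arguably acting off protocol. A site that uses the EOS page instead turns an early value into an apparent week-16 one. Sites may well differ.

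Skin tolerability over 16 weeks and change in ADCS-ADL SIV are both secondary objectives. Application-site reactions are one of the stated reasons for the study's safety assessments (Protocol 1.2). At stake is whether the graded skin, adhesion and functional summaries describe the treated patients or mainly those who stayed on treatment long enough to reach a scheduled visit.

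**Working it through.** **Inputs from the documents.** Enrolment of 102 and dropout of 10% (Protocol 8.7, SAP 8.6); visit timing (both schedules); N and percentage base (SAP 8.1, Table 14.3.8); no imputation of safety data, and LOCF at week 16 (SAP 8.5.1).

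**Assumed, because the documents give no values.** The number k stopping before Visit 2 without a score: 5, 10 or 20. The reaction rate q among those assessed at Visit 2: 20%, range 10% to 30%. The mean ADCS-ADL SIV change D among patients with a week-16 score: −2.0, range −1.0 to −3.0. All 102 enrolled are taken to be in the analysis set.

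**1. The plan's own figures.** n = z²p(1−p)/(0.10p)² = 1.645² × 0.746 × 0.254 / 0.0746² = 92.1, so 93. Then 93 × 1.10 = 102.3, which gives the stated 102 when rounded down. Ten percent of 102 is 10.2, about 10 patients. Nothing says when they leave or why.

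**2. What the schedule yields if followed as written.**

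| Outcome | Stops before Visit 2 | Stops at Visit 2 | Stops between Visit 2 and EOS |
|---|---|---|---|
| Skin, adhesion, CMQ | no score | Visit 2 score | Visit 2 score only |
| MMSE, urine | baseline only | Visit 2 score | Visit 2 score only |
| ADCS-ADL SIV | baseline only | baseline only | baseline only |

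For skin and adhesion the gap concerns stops before Visit 2. For ADCS-ADL SIV it concerns every stop before EOS. That includes a stop at week 8, where Protocol 3.1 says the physician "may consider continuing or changing the therapy".

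**3. Dilution of the Visit 2 skin row.** Percentage shown = q(102 − k)/102. With q = 20%:
- k = 5: 0.20 × 97/102 = 19.0%
- k = 10: 0.20 × 92/102 = 18.0%
- k = 20: 0.20 × 82/102 = 16.1%

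With k = 10 and q from 10% to 30%, the row shows 9.0% to 27.1%.

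**4. A different quantity: patients with a reaction by Visit 2, counting the unscored.** If all k had reacted, (q(102 − k) + k)/102 gives 23.9%, 27.8% and 35.7% for k = 5, 10 and 20 at q = 20%. If none had, the values are those in step 3. This is a cumulative proportion, not the Visit 2 row, and no current table shows it for graded scores.

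**5. ADCS-ADL SIV under LOCF.** For this step let k be the number stopping before EOS with no recorded post-baseline score on the scale.
- If they are in the ITT set and baseline is carried, each contributes a change of 0 and the mean is D(102 − k)/102. With D = −2.0 this is −1.90, −1.80 and −1.61 for k = 5, 10 and 20. With k = 10 and D from −1.0 to −3.0, it is −0.90 to −2.71.
- If they are left out, the mean stays at D.
- If the site used the EOS page, the early score is printed as EOS.

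The documents do not choose among these three.

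**The case against.** The strongest reply is that treatment-stopping reactions are not lost. The primary analysis is adverse events (SAP 9.6.1). Events may be volunteered between visits (Protocol 6.1), and safety contact continues for 30 days after the last visit or dose (Protocol section 5). A reaction recorded as an AE reaches Tables 14.3.1 to 14.3.6, including the row for events leading to discontinuation of study medication, whatever the visit. This stands. What is lost is the graded skin score, the adhesion score and the caregiver data.

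A reader might infer that early stoppers simply drop out of the functional results. The documents do not support that: LOCF covers week 16, and ITT membership needs only one assessment of any kind after baseline. The result is undetermined, not necessarily an exclusion.

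A reader might also take the step 4 percentages as the error in the Visit 2 row, or take the roughly 10 points implied by 10 of 102 as a ceiling. Neither holds. Step 4 is cumulative. The 10% is a planning allowance with no timing: more early stops would widen the gap, and stops after Visit 2 would not affect that row. Nor do the documents show that stops concentrate in patients with poor skin tolerability, since Protocol 4.6.6 allows interruptions and dose adjustments to keep patients on drug.

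Finally, the CRF (Final 2.0, cited in SAP section 5) was not available for this review and may contain an early-termination page. The listings are to cover all CRF variables, so individual data would be listed if collected. That would ease the collection gap but supply neither a table row nor a mapping rule.

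**Conclusion.** The point holds in this form: the early discontinuation assessment is required but undefined, and the SAP has no place for it. Patients who stop before Visit 2 have no scheduled graded skin or adhesion score, yet remain in the denominator of Table 14.3.8. The week-16 ADCS-ADL SIV result for any early stopper depends on a choice that the plan does not make.

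The size cannot be derived from the documents. Under the stated assumptions, 10 early stoppers move a 20% Visit 2 reaction rate to 18.0%, and carrying baseline moves a mean ADCS-ADL SIV change of −2.0 to −1.80. Both shrink by 10/102, or 9.8% in relative terms. These are secondary, descriptive summaries in a study with no hypothesis (Protocol 8.4.2), and the primary AE analysis is largely unaffected for reactions recorded as AEs. The change is still worth making, because these patients are already being asked to return.

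**What to change.** **Protocol and SAP schedules.** Add an early-discontinuation column with the Visit 3 assessments, including ADCS-ADL SIV, MMSE, skin irritation, adhesion, CMQ and urine. State that it also applies when treatment is stopped at Visit 2, so that ADCS-ADL SIV is obtained then.

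**SAP tables.** Add a labelled early-discontinuation row to the affected shells (14.2.1, 14.2.2.1, 14.2.3, 14.3.8 and 14.3.10 to 14.3.14). In Table 14.3.8, base the by-visit skin and adhesion percentages on patients assessed at that visit. Add a row for any reaction, or the worst score, at any assessment over the 16 weeks. A separate early-discontinuation row alone would not give that cumulative figure.

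**SAP 8.5.1.** Use the early-discontinuation MMSE and ADCS-ADL SIV scores as the last post-baseline observation for week 16. State that baseline is not carried forward. Do not print early scores as observed EOS values.

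**Cost.** EOS forms for roughly 10 patients (the planned 10% dropout) and slightly longer tables. If data collection is already complete, the schedule change comes too late, but the mapping rule, rows, denominators and LOCF statement can still be set before database lock.
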